CSF PGRN Concentrations: A statistically significant increase in CSF PGRN levels (compared to baseline) was seen at both post-dose time points for each of these 3 cohorts (Day 2 and Day 13). The maximum increase in CSF PGRN was observed 12 days after dosing: 1.57 times for 15 mg/kg, 1.84 times for 30 mg/kg, and 2.11 times for 60 mg/kg compared to baseline. No statistically different changes in CSF PGRN levels have been observed in subjects that received placebo. In the 60 mg/kg expansion cohort, 24 days after dosing, the PGRN level was increased 1.83-fold over baseline and 42 days after dosing the PGRN level was increased 1.23-fold over baseline. Coefficients of variation were in the range of 20% to 40% for the 30 mg/kg and 60 mg/kg cohorts over the cited sampling period.

Safety: AL001 was generally safe and well tolerated through the highest dose assessed (60 mg/kg), without dose-limiting toxicities or apparent trends in adverse events (AEs).

Part 2, Patients with Asymptomatic FTD-*GRN* or Symptomatic FTD-*GRN*

The second part of the study was conducted in two cohorts: the first cohort assessed safety, PK, and PD after a single-dose of AL001 in asymptomatic carriers of a loss-of-function *GRN* mutation causative of FTD (asymptomatic FTD-*GRN*); while the second cohort assessed safety,

PK, and PD after repetitive dosing in symptomatic FTD carriers of a loss-of-function *GRN* mutation (symptomatic FTD-*GRN*). A total of 6 asymptomatic FTD-*GRN* participants and 8 symptomatic FTD-*GRN* participants were enrolled and completed dosing in the second portion of the study. Asymptomatic FTD-*GRN* participants were administered a single IV dose of AL001 at 60 mg/kg and symptomatic FTD-*GRN* participants were administered 3 doses of IV AL001 30 mg/kg, q2w.

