3.3. Description of Study Periods

3.3.1. Part 1 – Treatment Period

Screening

Participants may be consented and screened within 6 weeks prior to Day 1 to determine eligibility.

Treatment Period and Follow-up Period

The planned study treatment period will be a total of 96 weeks. AL001 60 mg/kg will be administered intravenously q4w for a total of 25 doses (up to and including Week 97). Cognitive and functional testing ([Section 6.9](#)), which may include input from the participant and study partner (study partner is described in [Section 4.1.1](#)), will be performed during screening and then every 12 weeks. Imaging will be performed during screening and then every 24 weeks. Lumbar puncture for CSF collection will be performed at screening and then every 24 weeks. Accepted windows for treatment, clinical assessments, and imaging are provided in the Schedules of Assessments ([Table 4](#), [Table 5](#), [Table 6](#), [Table 7](#), [Table 8](#), and [Table 9](#)).

Every effort will be made to follow all enrolled participants for the full 96-week treatment period, irrespective of whether they discontinue study treatment. All participants will be followed for safety at 10 weeks after the last dose of AL001.

Upon completion of the 96-week treatment period, participants who are eligible and provide consent will continue in Part 2 (Optional OLE) of the study (Continuation from Week 97 to Week 101). Participants who do not continue in Part 2 (Optional OLE) will return to the investigational site 10 weeks after their last dose of AL001 for final safety assessments.

In this protocol (Study AL001-2), the term “study drug” refers to AL001.

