4.3.1. Part 1 (Treatment Period)

4.3.1.1. Withdrawal from Study Drug (Part1)

A participant may be discontinued from study drug at any time if the participant or the investigator feels that it is not in the participant's best interest to continue. The following is a list of possible reasons for study drug discontinuation:

1. Participant is noncompliant with the protocol
2. Participant is lost to follow-up
3. Participant withdraws consent
4. Participant has a serious or intolerable AE that, in the investigator' opinion, requires withdrawal from the study drug
5. Serum aminotransferase levels (ALT or AST) $>3 \times$ ULN AND total bilirubin $>2 \times$ ULN without an alternative explanation
6. Anaphylaxis
7. Infusion-related or injection-related reaction despite adequate premedication for an initial occurrence of a moderate to severe infusion-related reaction ([Section 5.1.2](#)) or if the participant experiences any of the following events: mucosal tissue involvement, airway compromise, or symptomatic hypotension with systolic blood pressure <90 mm Hg measured in the supine position
8. Occurrence of an intercurrent illness that, in the investigator's opinion, will affect assessments of clinical status or safety to a significant degree
9. Use of a nonpermitted concomitant medication per [Section 4.1.2](#) (as appropriate)
10. Pregnancy
11. Discretion of the investigator

If a participant is withdrawn from study drug due to an AE or SAE, the participant will be followed up by the investigator until the abnormal parameter or symptom has resolved or stabilized (if applicable). The investigator has the responsibility for all decisions regarding participant safety. It is recommended that the investigator consult with the Medical Monitor prior to removing the participant from study drug for any reason except participant withdrawal of consent and in case of medical emergency. If a participant is discontinued because of an AE or SAE, the event will be followed up until it is resolved. Any participant may withdraw his or her consent at any time.

All participants who discontinue study drug prior to the completion of the Part 1 96-week treatment period should be encouraged to complete all remaining scheduled assessment visits through the Part 1 treatment period (Week 97). Study staff will follow-up to aid in this goal.

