6.11. Part 1 End of Treatment Visit

Participants who discontinue study drug prior to completing the 96-week Part 1 treatment period should be encouraged to complete all remaining scheduled assessment visits through Part 1 (including COAs, MRI, and CSF evaluations).

A Part 1 EOT visit will only be completed by participants who discontinue study drug but remain in Part 1 of the study and continue to perform all assessments ([Section 4.3.1.1](#)). Part 1 EOT assessments should be completed as soon as possible after the decision is made.

The EOT visit may be substituted by a scheduled study visit if it occurs within the same window.

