6.13. Safety Follow-up Visit

A Safety Follow-up visit will be performed 10-weeks following the last dose of AL001. The Safety Follow-up visit may be substituted by a scheduled visit if it occurs within the same window.

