2.3.4. Full Analysis Population

The Full analysis population will include all participants in the safety population who had both a baseline and at least 1 postdose PD assessment. The Full analysis population will be used for summaries of all PD and PD biomarker summaries.

3. Participant Disposition and Protocol Deviations

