10.1. Analysis visit windows

The following analysis visit windows will be used for all PD biomarker analyses:

Study day	Analysis Visit
Less or equal to 1	Baseline
Between 2 and 20	Week 2
Between 21 and 43	Week 5
Between 44 and 71	Week 9
Between 72 and 99	Week 13
Between 100 and 127	Week 17
Between 128 and 155	Week 21
Between 156 and 183	Week 25
Between 184 and 211	Week 29
Between 212 and 239	Week 33
Between 240 and 267	Week 37
Between 268 and 295	Week 41
Between 296 and 323	Week 45
Between 324 and 351	Week 49
Between 352 and 393	Week 53
Between 394 and 463	Week 61
Between 464 and 547	Week 73
Between 548 and 631	Week 85
Between 632 and 757	Week 97
Between 758 and 925	Week 121
Between 926 and 1093	Week 145
Between 1094 and 1275	Week 169
Greater than or equal to 1276	Week 197

All PD biomarker analyses will be conducted with one data point per time point and subject. If the measurement is available for the nominal time, its value will be used in the analyses. If the measurement for a nominal time point is missing and measurements for unscheduled visits that fall in the corresponding analysis window are available, the value from the sample collected closest to the nominal time point will be used.

10.2. Exploratory Pharmacodynamic Biomarkers of Neurodegeneration, lysosomal function, and glial activity

Exploratory plasma and CSF PD biomarker samples are collected for evaluation for neurodegeneration (e.g., neurofilament-light chain [NfL]), lysosomal function (e.g., cathepsins), and glial activity (e.g., YKL 40, GFAP), and to potentially evaluate levels of other analytes relevant to disease biology and response to AL001. CSF PD biomarker samples are collected in Part 1 only. The timepoint at which the exploratory PD biomarkers of neurodegeneration are identified in [Appendix 14.1](#), [Appendix 14.2](#), [Appendix 14.4](#) and [Appendix 14.5](#).

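### Part 1 by-visit PGRN, biomarker and AL001 concentration summaries carry no on-drug condition, so washout samples can be averaged with on-dosing samples

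*SAP*

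**What the plan says.** **Follow-up after stopping drug.** Protocol 3.3.1 states: "Every effort will be made to follow all enrolled participants for the full 96-week treatment period, irrespective of whether they discontinue study treatment". Protocol 4.3.1.1 and 6.11 add that people who stop are encouraged to attend every remaining Part 1 visit, and 6.11 names CSF among the assessments. For the visit due 10 weeks after the last dose, Protocol 6.13 says: "The Safety Follow-up visit may be substituted by a scheduled visit if it occurs within the same window".

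**Who is summarized.** SAP 2.3.4: "The Full analysis population will include all participants in the safety population who had both a baseline and at least 1 postdose PD assessment". There is no on-treatment condition.

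**What is summarized.** SAP 8.1 and 8.2 summarize plasma and CSF PGRN by cohort and timepoint. SAP 10.2 does the same for the exploratory biomarkers by visit and cohort. SAP 7.1 and 7.2 summarize serum and CSF AL001 concentrations by visit, with values below quantification set to zero.

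**Which value is used.** SAP 10.1 opens: "The following analysis visit windows will be used for all PD biomarker analyses". It then gives the selection rule: "If the measurement is available for the nominal time, its value will be used in the analyses". Only if the nominal value is missing does it turn to unscheduled visits inside the window, taking the sample closest to the nominal time.

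**What is silent.** SAP 5.3 ends exposure 28 days after the last dose, but uses that limit only for exposure duration. Nothing applies it to PK or PD samples, and nothing says that a summary regardless of discontinuation is intended.

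**The concern.** PGRN rises while Sortilin is blocked and falls when dosing stops. A Week 49 sample from someone who stopped at Week 25 measures washout, yet under the plan it enters the Week 49 mean alongside predose values from people still on drug. A reader of the table cannot tell a falling mean caused by stopped dosing from a waning effect under dosing.

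This matters more because SAP 12 drops the Sortilin assay for sample instability and names plasma and CSF PGRN as the target-engagement marker. The same values feed the SAP 10.4 correlations of Week 49 biomarker change with change in the CDR plus NACC FTLD Sum of Boxes. The cohorts are small (up to 20 per mutation, with the GRN group split again by symptom status), so one or two people can move a visit mean.

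**Working it through.** The plan gives no figure for this point, so there is none to reproduce. The check has five steps.

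**1. Does the chain hold?** Off-drug samples are collected by design in Part 1 (Protocol 3.3.1, 4.3.1.1, 6.11). The population does not remove them (SAP 2.3.4), and neither do the summaries (SAP 7.1, 7.2, 8.1, 8.2, 10.2) or the value-selection rule (SAP 10.1). The sentence in 10.1 does not cause the mixing alone; it does so together with the follow-up rule and the missing on-drug condition. It stands in the exploratory section but is worded for all PD biomarker analyses. If it were held not to reach PGRN, SAP 8 would still contain no on-drug condition.

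**2. How many samples can one person add?** Study day = 1 + 7 × (week − 1). The counts are scheduled Part 1 plasma PGRN visits more than 28 days after the last dose, assuming full attendance.

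| Last dose | Off-drug PGRN visits |
|---|---|
| Week 13 | 13 |
| Week 25 | 10 |
| Week 49 | 4 |
| Week 73 | 2 |

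A limit of 42 days gives the same counts, because nominal visits fall 28 days and then at least 56 days after the last dose. For CSF, a last dose at Week 25 (day 169) puts the Week 49 sample (day 337) 168 days later.

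**3. Where do follow-up samples land?** Follow-up day = last-dose day + 70.
- Last dose Week 25: 169 + 70 = day 239, inside the Week 33 window (212 to 239).
- Last dose Week 97: 673 + 70 = day 743, inside the Week 97 window (632 to 757).

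The SAP does not say whether end-of-treatment, end-of-study and follow-up samples are mapped to these windows. SAP 8.2 lists the end-of-treatment or end-of-study CSF sample as an alternative to Week 97.

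**4. What interval is compatible with dosing on schedule?** Visits are fixed from Day 1 and each has ±7 days. A dose 7 days early followed by a predose sample 7 days late is 28 + 7 + 7 = 42 days apart, with no deviation.

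**5. How large could the dilution be?** Protocol 1.2.2.1 reports CSF PGRN in healthy volunteers after one 60 mg/kg dose as 1.83-fold at 24 days; "42 days after dosing the PGRN level was increased 1.23-fold over baseline". With f the off-drug share (assumed), the mean rise in percent is (1 − f) × on + f × off.

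| f | on 83, off 23 | on 83, off 0 | on 62, off 23 |
|---|---|---|---|
| 10% | 74.7 + 2.3 = 77 | 75 | 58 |
| 20% | 66.4 + 4.6 = 71 | 66 | 54 |
| 40% | 49.8 + 9.2 = 59 | 50 | 46 |

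The value 62 is the day-28 rise if the excess decays log-linearly between the two reported points. The rate is ln(0.83/0.23)/18 = 0.0713 per day, a half-life of 9.7 days. The day-28 excess is 0.83 × exp(−0.0713 × 4) = 0.62. At day 70 it is 0.83 × exp(−0.0713 × 46) = 0.03, or about 1.03-fold, so samples 10 weeks off drug would be near baseline. The 1.23-fold value lies at the edge of compliant dosing (42 days), so longer gaps would dilute more than the first column shows.

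**The case against.** The case against is substantial.

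- Summarizing all observed data is a legitimate choice in a descriptive study without formal testing. Individual PGRN is listed and plotted against actual time, and dosing is listed, so off-drug values can be traced. For PGRN the error understates the effect, so it would not create a false claim of target engagement. All of this stands. But the SAP does not say that it made this choice, and a listing does not repair a by-visit mean. Ending cohort figures at Week 49 leaves the tables, and Week 49 itself, as they are.
- A reader might infer that the high attrition reported in SAP 2 means late means have been pulled down. The documents do not support that. People who leave the study give no later samples; dilution needs people who stop drug and stay, and their number is not given. It may be small, since attendance is encouraged and not assured.
- A reader might infer that any sample in a window fills a gap. SAP 10.1 allows only unscheduled visits. End-of-treatment and follow-up samples are therefore unassigned; they are not shown to enter regular visits.
- A reader might extend the point to all PK results. SAP 7.3 treats values below quantification after the first measurable one as missing when parameters are derived, so the zero rule affects only the concentration summaries. End-of-infusion samples cannot be off drug.
- A reader might extend it to Part 2. There, people who stop drug leave through an end-of-study visit (Protocol 6.12.2).
- The healthy-volunteer decay is a weak reference for repeat-dosed carriers. In AL001-1, symptomatic carriers had CSF PGRN of 3.76 against a baseline mean of 1.82 ng/mL (3.76/1.82 = 2.1-fold) 28 days after a third 30 mg/kg dose. The illustration is an assumption, not an estimate.

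**Conclusion.** The gap is real and confined to Part 1. As written, the plan lets samples taken after AL001 was stopped, or after missed doses, enter by-visit summaries of plasma PGRN, CSF PGRN, exploratory biomarkers and AL001 concentrations, and the Week 49 correlations. For PGRN the expected direction is towards understating target engagement.

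The size cannot be stated from the documents. The range of +77% to +59% in place of +83% rests on two assumptions: off-drug shares of 10% to 40%, and single-dose healthy-volunteer CSF values that carry over to repeat-dosed carriers. The documents do not support the conclusion that any mean has in fact fallen for this reason.

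**What to change.** In SAP 7.1, 7.2, 8 and 10:

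1. Derive days since last AL001 dose for every post-baseline PK and PD sample.
2. Make the main by-visit PGRN and drug-concentration summaries, and the PGRN Week 49 correlation, on-treatment: no more than 42 days since last dose (the 28-day interval plus the 7-day window on both visits) and not after permanent discontinuation. A 35-day limit counts only one of the two windows. It would remove low predose values from compliant participants and bias PGRN upward.
3. Report the off-drug n at each visit and keep the all-sample tables as supportive.
4. State that end-of-treatment, end-of-study and Safety Follow-up samples appear in their own rows and are not mapped into regular visits when off drug.

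The cost is one derived variable and an extra set of tables, from dose and sample dates already collected. The downside is a smaller n at late visits. This is a cheap improvement.

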4. PARTICIPANT SELECTION AND WITHDRAWAL CRITERIA

4.1. Part 1 Study Population

Approximately 40 participants will be enrolled at approximately 13 investigational sites in North America and Europe. Two cohorts will be enrolled in Part 1 (Treatment Period):

- *GRN* mutation Cohort (up to 20 asymptomatic and symptomatic participants), including:
 - All asymptomatic and symptomatic participants in Study AL001-1 may be enrolled.
 - New symptomatic *GRN* mutation carriers may be enrolled.
- *C9orf72* mutation Cohort (up to 20 new symptomatic participants).

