9.8. Optional Winterlight Labs Speech Assessments

The optional WLA will be analyzed and reported outside of this SAP.

10. Exploratory Pharmacodynamic Biomarkers

All analyses of exploratory PD biomarker data will be conducted using the Full analysis population.

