For all biomarkers listed in the following table, the absolute value, absolute change, percent change from baseline, and ratio to baseline values for exploratory biomarker parameters will be summarized by visit and cohort using descriptive statistics, including the number of participants, mean, SD, median, min and max. Additionally, for absolute value and ratio to baseline, geometric mean (calculated as $\exp(\text{mean}(\log(\text{absolute value or ratio to baseline})))$) and geometric SD will be summarized. For NfL and GFAP, mean absolute value, mean percent change from baseline values, and geometric mean ratio to baseline plus or minus the SD, will also be plotted versus nominal time points up to Week 49. All biomarker concentration values that are BLQ will be set to $\frac{1}{2}$ of LLOQ when calculating summary statistics. In the case of Vendor not providing LLOQ, such as Cell Carta, data points with results being 0 will be excluded from the analysis.

Exploratory Pharmacodynamic Biomarkers		
C1Qb	[REDACTED]	[REDACTED]
C1Qc	[REDACTED]	[REDACTED]
[REDACTED]	[REDACTED]	[REDACTED]
[REDACTED]	[REDACTED]	YKL40
CTSD	LAMP1	[REDACTED]
[REDACTED]	[REDACTED]	MIF
[REDACTED]	[REDACTED]	[REDACTED]
[REDACTED]	[REDACTED]	GFAP
[REDACTED]	[REDACTED]	[REDACTED]

- For the GFAP analysis, only GFAP data from Quanterix will be used. Data on CSF GFAP initially obtained on the Roche NTK platform will be excluded from the data analysis, as those samples were subsequently re-analyzed on the Quanterix SIMOA platform. At the time of analysis, Roche did not have the capability to analyze plasma samples for GFAP. Since plasma GFAP was analyzed on the Quanterix platform, all GFAP (plasma and CSF) analyses were ultimately conducted on the Quanterix platform in order to maintain consistency between matrices.

- For the biomarker data obtained from Cell Carta, each biomarker was assayed with 7 different peptides. The analysis will only include data from the peptide recommended by the Vendor for each biomarker for analysis. The list of recommended peptides is shown in the following table:

Protein	
C1qB	C1QB_HUMAN_IAFSATR_y4+
C1qC	C1QC_HUMAN_FQSVFTVTR_b2+
CTSD	CATD_HUMAN_VSTLPAITLK_y7+
LAMP1	LAMP1_HUMAN_AFSVNIFK_y6+

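### SAP 10.2 drops results of 0 from vendors without an LLOQ; if those zeros are nondetects, visit summaries read too high and change from baseline is pulled toward no change

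*SAP*

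**What the plan says.** SAP 10.2 gives two rules for low results. The general rule is "All biomarker concentration values that are BLQ will be set to" half the LLOQ for summary statistics. The next sentence makes the exception: "In the case of Vendor not providing LLOQ, such as Cell Carta, data points with results being 0 will be excluded from the analysis".

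The same section says "For the biomarker data obtained from Cell Carta, each biomarker was assayed with 7 different peptides", with one vendor-recommended peptide used per protein. The proteins legible in that table are C1qB, C1qC, CTSD and LAMP1.

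The outputs affected are descriptive: "the absolute value, absolute change, percent change from baseline, and ratio to baseline values for exploratory biomarker parameters will be summarized by visit and cohort". They include mean and median, and "for absolute value and ratio to baseline, geometric mean (calculated as" the exponential of the mean log) is added. The section does not say whether a 0 is a nondetect or a failed measurement. It plans no count of excluded zeros and no sensitivity analysis.

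The SAP's other rules for summarising concentrations keep the low value. Serum and CSF AL001 results below the limit are set to zero (SAP 7.1, 7.2), and plasma and CSF PGRN results are set to half the LLOQ (SAP 8.1, 8.2).

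**The concern.** A nondetect carries information: the true value lies below what the assay can see. Deleting it is selection on the outcome, and it acts only on the low tail. Three things follow if the zeros are nondetects.

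- Visit-level means, medians and geometric means are computed on the higher part of the distribution and read too high.
- A participant with a 0 at baseline loses every change value for that marker. A participant who falls to 0 on treatment loses that visit. If the marker falls, more post-dose than baseline values are deleted; if it rises, the reverse. Either way the change is pulled toward none.
- The number of participants by visit varies for a reason tied to the value, and the table does not show that reason.

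Cohorts are small: GRN is "up to 20 asymptomatic and symptomatic participants", which the SAP splits in two, and C9orf72 is "up to 20 new symptomatic participants". SAP Section 2 also reports high attrition. A few deletions can move a cohort summary.

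**Working it through.** The documents give no number of zeros, no detection limit, no SD and no expected change for these markers, so there is no plan figure to reproduce. All inputs below are assumptions.

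**1. Small example.** Ten participants have a baseline of 100. After dosing, k of them read 0 and the rest read 80. The assumed limit is 20, so half is 10 (a change of -90%).

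- Exclusion: mean change is -20% whatever k is.
- Half-limit, k = 1: (9 × -20 + 1 × -90)/10 = -27%.
- Half-limit, k = 2: (8 × -20 + 2 × -90)/10 = -34%.
- Half-limit, k = 3: (7 × -20 + 3 × -90)/10 = -41%.

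Under exclusion the summary does not respond to how many participants became undetectable.

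**2. Lognormal model, zeros as nondetects.** Between-person log-SD is 0.5 and within-person 0.25, so the total is s = √(0.5² + 0.25²) = 0.559. The true ratio is 0.70 (ln 0.70 = -0.357). The baseline median is 1 (log 0). The log detection limit L sits at the 5th or 10th baseline percentile.

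- Standardised limit on treatment: a = (L + 0.357)/s
- Zeros on treatment: Φ(a)
- Geometric mean after exclusion, relative to truth: exp{s·φ(a)/[1 - Φ(a)]}
- Median after exclusion, relative to truth: exp{s·Φ⁻¹([1 + Φ(a)]/2)}

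| | 5% baseline zeros | 10% baseline zeros |
|---|---|---|
| L | -1.645 × 0.559 = -0.920 | -1.282 × 0.559 = -0.716 |
| a | -1.007 | -0.643 |
| Zeros on treatment | 16% | 26% |
| Geometric mean | exp(0.559 × 0.2403/0.843) = 1.17 | exp(0.559 × 0.3243/0.740) = 1.28 |
| Median | exp(0.559 × 0.198) = 1.12 | exp(0.559 × 0.332) = 1.20 |

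The median of the absolute values with zeros ranked lowest is unaffected while zeros are fewer than half, because the order at the middle does not change.

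**3. The planned change measure.** SAP 10.2 summarises ratio to baseline within participant. Simulated pairs under the same model (2 million per setting) give:

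| True ratio 0.70 | 5% baseline zeros | 10% baseline zeros |
|---|---|---|
| Pairs lost under exclusion | 17% | 27% |
| Paired geometric mean ratio, exclusion | 0.72 | 0.73 |
| Paired geometric mean ratio, zeros at half the limit | 0.67 | 0.67 |

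Half-limit substitution also puts the on-treatment geometric mean 6-9% too low.

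**4. Other conditions.**

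- 1% baseline zeros, true ratio 0.70: the paired ratio reads 0.71.
- No true change, 5-10% zeros: the paired geometric mean ratio is 1.00, and mean percent change moves by less than one point. Absolute geometric means still read 6-12% high: exp(0.559 × 0.1031/0.95) = 1.06 and exp(0.559 × 0.1755/0.90) = 1.12.
- True ratio 1.30: exclusion gives 1.29 and 1.28, so the rise is understated.
- Zeros as random failures, 10% at each visit, true ratio 0.70 (within-person log-SD 0.3): the paired ratio reads 0.700.

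**5. Weakness of substitution.** Ten participants all read 80 after dosing; nine have a baseline of 100 and one has 0. If the lowest non-zero value is 20, the zero becomes 10 and that participant shows +700%. Mean percent change goes from -20% to (9 × -20 + 700)/10 = +52%.

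**The case against.** The exception has a reason. Without an LLOQ, half the LLOQ cannot be computed. A geometric mean cannot take a 0, and percent change or ratio from a 0 baseline is undefined. SAP 7.3 also treats some values below the limit as missing, although that is for deriving PK parameters and not for summarising concentrations. All of this stands, and it means the difference between vendors is not arbitrary. It does not require deletion everywhere: a median needs only the order of the values, and the lowest non-zero value is available from the data.

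A reader might infer that falls on AL001 will be understated. The documents do not support that. It needs zeros to occur, to be nondetects, and the marker to fall, and none of these is stated.

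A reader might also take all four proteins to be named for the lysosomal and glial objective. SAP 10.2 names cathepsins, which covers CTSD; C1q and LAMP1 appear only in its tables. The planned fluid-biomarker plots use NfL and GFAP, and the correlation analyses use PGRN, NfL and GFAP, so none of the four enters either.

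Two further points stand. On the paired geometric mean ratio, half-value substitution errs about as far below the truth as exclusion errs above it. And by-visit n is tabulated, all collected data are listed (SAP Section 2), and no formal testing is planned. The listings do keep the zeros, but a falling n does not tell a table reader that low values were removed.

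**Conclusion.** The point holds in conditional form. If a 0 is a nondetect, the rule deletes values because they are low. At 5-10% baseline zeros and a true ratio of 0.70, the on-treatment median is 12-20% too high and the geometric mean 17-28% too high. The planned paired geometric mean ratio is less affected, at 0.72-0.73. A rise would be understated in the same way. There is no bias if zeros are random failures or do not occur. If there is no true change, the paired ratio is unbiased although the absolute levels still read high.

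The sizes rest on the assumed lognormal SDs, zero frequency and true ratio. The direction rests on what a Cell Carta 0 means, which the documents leave open. The endpoints are exploratory and descriptive, so this is a low-priority correction.

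**What to change.** In SAP 10.2:

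1. Confirm with the vendor what a 0 means, state it, and treat only failed measurements as missing.
2. Keep nondetect zeros in the medians, ranked lowest.
3. Show the number of zeros by visit and cohort.
4. For geometric means and change measures, present the exclusion result beside a sensitivity analysis that sets zeros to half the lowest non-zero value for that peptide and matrix.

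The cost is one vendor query, a few SAP sentences, one count row and a second set of summaries for these markers. The downside is that the substituted value is arbitrary and has its own error (paired ratio about 0.67 against a true 0.70). A substituted baseline can also inflate mean percent change in a small cohort. For that reason it should stand beside the exclusion result as a sensitivity analysis and not replace it.
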